15.3 Slit-Lamp Biomicroscopy Examination

A slit-lamp biomicroscopy examination of the cornea, conjunctiva, anterior chamber, iris, lens, lid, motility and pupil will be performed at pre- and post-treatment at Visit 1 and may be performed post-CAE® at Visit 2 at the Investigator's discretion as needed. The results will be graded as Normal, Abnormal Not Clinically Significant (NCS) or Abnormal Clinically Significant (CS). Abnormal findings will be described.

The results will be summarized using counts and percentages for each treatment group at each visit for each eye (study eye and fellow eye). Percentages will be based on the number of subjects in each treatment group with responses. Shift tables for the slit-lamp biomicroscopy parameters will also be provided comparing post-treatment at Visit 1 and post-CAE® at Visit 2 to baseline. A subject listing of the slit-lamp biomicroscopy parameters will also be produced.

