8.3 Examination Procedures

8.3.1 Procedures to be Performed at Each Study Visit with Regard to Study Objectives(s)

The following procedures will be performed (see [Appendix 2](#) for description).

Visit 1 (Day 1): Screening and Schirmer's Test Evaluation

Screening

- Informed consent/Health Information Portability and Accountability Act (HIPAA) consent
- Demographic data, medical/medication, and ocular history
- Eligibility Criteria
- OSDI©
- EDS (visual analog scale)
- ██████████ Ocular Discomfort Scale
- BCVA
- Slit lamp biomicroscopy
- Corneal fluorescein staining
- Schirmer's Test³
- Schirmer's Test with nasal stimulation (cotton swab)⁴
- Intranasal examination
- Urine Pregnancy Test (if applicable)
- Concomitant Medications
- AE Query

Treatment (Schirmer's Test Evaluation)

Pre-Treatment Procedures:

- Randomization: Qualified participants will be assigned to one of the following treatment groups:
 - Placebo (vehicle) delivered as a 100 µL intranasal spray in each nostril
 - 0.11% OC-02 (0.2% hemigalactarate salt) delivered as a 100 µL intranasal spray in each nostril

³ Procedure will occur after corneal fluorescein staining

⁴ Schirmer's test with nasal stimulation will occur 10 minutes after the first Schirmer's test

- 0.55% OC-02 (1.0% hemigalactarate salt) delivered as a 100 µL intranasal spray in each nostril
- 1.1% OC-02 (2.0% hemigalactarate salt) delivered as a 100 µL intranasal spray in each nostril

Treatment Procedures:

- Instruct subjects on investigational drug / placebo administration
- Treatment with investigational drug/placebo

Post-Treatment Procedures:

- Post-treatment Schirmer's test (performed immediately after investigational drug administration)
- BCVA
- Slit lamp biomicroscopy
- Intranasal endoscopic examination
- Concomitant Medications
- AE Query
- Schedule participant for Visit 2

Visit 2 (Day 15+4): CAE

- Medical/medication and ocular history updates
- EDS
- Ora Calibra® Ocular Discomfort Scale
- Approximately 120 minutes of CAE® Exposure
- EDS collected upon entering the CAE® and every 5 minutes thereafter.
- ██████████ Ocular Discomfort Scale upon entering the CAE® and every 5 minutes thereafter.
- Instruct subjects on investigational drug/placebo administration
- Treatment with investigational drug/placebo

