 - Treatment with Investigational drug/placebo will be administered upon participant reporting an Ocular Discomfort score ≥ 3 at two or more consecutive time points in at least one eye during CAE® exposure (if a participant has an Ocular Discomfort rating of 3 at time = 0 for an eye, s/he must report an Ocular Discomfort rating of 4 for two consecutive measurements for that eye) using the ██████████ Scale. Participant will resume symptom assessments 1 minute after the application ends every 5 minutes.
- BCVA
- Slit lamp biomicroscopy

- Intranasal Examination
- Urine Pregnancy Test (if applicable)
- Concomitant Medications
- AE Query
- Study exit

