13 APPENDICES

APPENDIX 1: SCHEDULE OF VISITS AND MEASUREMENTS

Procedure	Visit 1 (Day 1)		Visit 2 (Day 15 + 4)	
	Screening	Schirmer's Test Evaluation	Pre-CAE®	Post-CAE®
Informed consent/HIPAA	X			
Demographics	X			
Medical/Medication, ocular history and updates	X		X	
Eligibility criteria	X			
Urine pregnancy test	X ₃		X ₃	
OSDI® questionnaire	X			
Eye Dryness Score (EDS)	X		X ₄	X ₄
■ Ocular Discomfort Scale	X		X ₄	X ₄
BCVA	X	X ₁		X ₅
Slit lamp biomicroscopy	X	X ₁		X ₅
Corneal fluorescein staining	X			
Schirmer's test	X	X ₁		
Schirmer's test with cotton swab stimulation	X			
Intranasal examination	X	X ₁		X
Concomitant medications	X	X ₁		X
Randomization		X		
Administer investigational drug / placebo		X ₂	X	
AE Query	X	X ₁	X	X
Exit from study				X

X₁ = Post-treatment procedures; X₂ = Concurrent with Schirmer's Test; X₃ = For females of childbearing potential; X₄ = Procedure started at time 0 and then conducted every 5 minutes thereafter during the 120 minute CAE® exposure; X₅ = Procedure may be performed after CAE® exit at the Investigator's discretion as needed

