APPENDIX 2: EXAMINATION PROCEDURES, TESTS, EQUIPMENT, AND TECHNIQUES

The following examination procedures, tests, equipment and techniques are listed in this Appendix:

Visual Acuity Procedures

LogMAR visual acuity must be assessed using an ETDRS chart. The procedure used will be consistent with the recommendations provided for using the ETDRS eye chart. Visual acuity should be evaluated at the beginning of each visit in the study (i.e., prior to slit lamp examination). Participants should use the most recent correction to attain their corrected distance visual acuity (CDVA); if they forget their spectacles, this prescription can be placed in a trial frame.

Equipment

The visual acuity chart to be used is the ETDRS chart. If smaller reproduction (18" by 18", e.g., from Prevent Blindness) wall charts are used, the participant viewing distance should be exactly 10 feet (or as specified by the manufacturer). In ALL cases, for purposes of standardizing the testing conditions during the study, all sites must use only ETDRS Series 2000 Chart 1 & 2, and the right eye should be tested first. For reflectance (wall) charts, the chart should be placed frontally and be well illuminated.

Measurement Technique

The chart should be at a comfortable viewing angle. The right eye should be tested first. The participant should attempt to read each letter, line-by-line, left to right, beginning with line 1 at the top of the chart. The participant should be told that the chart has letters only, no numbers. If the participant reads a number, s/he should be reminded that the chart contains no numbers, and the examiner should then request a letter in lieu of the number. The participant should be asked to read slowly, so as to achieve the best identification of each letter. S/he is not to proceed to the next letter until s/he has given a definite response.

If the participant changes a response (e.g., 'that was a "C" not an "O"') before s/he has read aloud the next letter, then the change must be accepted. If the participant changes a response having read the next letter, then the change is not accepted. The examiner should never point to the chart or to specific letters on the chart during the test.

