A maximum effort should be made to identify each letter on the chart. When the participant says s/he cannot read a letter, s/he should be encouraged to guess. If the participant identifies a letter as one of two letters, s/he should be asked to choose one letter and, if necessary, to guess. When it becomes evident that no further meaningful readings can be made, despite encouragement to read or guess, the examiner should stop the test for that eye. However, all

letters on the last line should be attempted as letter difficulties vary and the last may be the only one read correctly. The number of letters missed or read incorrectly should be noted.

LogMAR Visual Acuity Calculations

The last line in which a letter is read correctly will be taken as the base logMAR reading. To this value will be added the number "N x 0.02" where 'N' represents the total number of letters missed up to and including the last line read. This total sum represents the logMAR visual acuity for that eye.

Example: Participant correctly reads 4 of 5 letters on the 0.2 line, and 2 of 5 letters on the 0.1 line.

Base logMAR	= 0.1
N (total number of letters incorrect on line 0.2 as well as 0.1)	= 4
N x T (T=0.02)	= 0.08
Base logMAR + (N x T)	= 0.1 + 0.08
logMAR visual acuity	= 0.18

Repeat the procedure for the left eye.

In order to provide standardized and well-controlled assessments of visual acuity during the study, all visual acuity assessments at a single site must be consistently done using the same lighting conditions and same correction if possible during the entire study. If the same correction cannot be used (i.e., a participant broke his/her glasses), the reason for the change in correction should be documented.

Note: A clinically significant visual acuity decrease (defined as an increase of 0.22 or greater in logMAR score) from the Screening Visit (Visit 1) should be evaluated by the Investigator as a potential AE.

Slit Lamp Biomicroscopy

Slit lamp biomicroscopy will be performed during the study. Observations will be graded as *Normal* or *Abnormal*. Abnormal findings, which are clinically significant, will be described. The following will be examined at each visit:

- Cornea
- Conjunctiva
- Anterior Chamber
- Lid

Corneal Fluorescein Staining

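### Protocol 8.3.1 requires acuity and slit-lamp exams at Visit 2, but schedule footnote X5 and SAP 15.2/15.3 make them optional and still tabulate the results

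*SAP*

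**What the plan says.** **Unconditional.** Protocol 8.3.1 opens its visit lists with "The following procedures will be performed". The Visit 2 list then contains BCVA and, directly after it, "Slit lamp biomicroscopy", neither with a qualifier. Protocol Appendix 2, under slit lamp, introduces the structures to be checked with "The following will be examined at each visit".

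**Discretionary.** Both exams carry footnote X5 in the Visit 2 post-CAE column of the schedule in Protocol Appendix 1, and X5 begins "Procedure may be performed after CAE". The rest of the footnote leaves the exam to the investigator's judgement of need. SAP 4.2 repeats it. SAP 15.3 contrasts the two visits in one sentence: "lens, lid, motility and pupil will be performed at pre- and post-treatment at Visit 1 and may be performed post-CAE". SAP 15.2 does the same for BCVA.

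**Still analysed.** SAP 15.2 summarises BCVA and its change from baseline by visit. SAP 15.3 gives slit-lamp counts and percentages at each visit, with the rule "Percentages will be based on the number of subjects in each treatment group with responses", and a shift table that includes post-CAE Visit 2 against baseline.

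**A safety check that relies on the exam.** Protocol Appendix 2 describes "A clinically significant visual acuity decrease (defined as an increase of 0.22 or greater in logMAR score", measured against the Screening Visit, and asks the investigator to evaluate it as a possible adverse event.

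**A parallel case.** SAP 15.4 attaches as-needed wording to the intranasal examination, although both schedules mark that examination at Visit 2 without X5.

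**The concern.** A site that follows 8.3.1 examines everyone at Visit 2. A site that follows X5 may examine only some. The visible text does not say which instruction prevails or when an exam counts as needed. It is also unclear whether an omitted exam is a protocol deviation: it would be one under 8.3.1 and not under X5.

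Visit 2 ends with study exit, so this is the only scheduled acuity and slit-lamp assessment after the second dose. If investigators examine mainly subjects who complain, abnormal percentages and mean acuity changes at Visit 2 come from a group chosen for having problems and would tend to look worse than the whole group. A loss of 0.22 logMAR or more that the subject does not mention could also go unmeasured. The tables will show how many were examined, through n and the category counts, but not what the unexamined subjects would have had.

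**Working it through.** **1. Is the discretion about whether to examine, or only about when?** SAP 15.2 and 15.3 say the exams will be done at Visit 1 and may be done at Visit 2, so it is about whether. The Visit 2 list in 8.3.1 does state conditions where they are meant: the pregnancy test is marked as applicable to some subjects only. BCVA and slit lamp have no such mark. The conflict is therefore in the text, and none of the conflicting text is redacted.

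**2. The plan's own figure.** Protocol 10.3 has 40 per arm with 5% dropout: 40 × (1 − 0.05) = 38 completers per arm, which reproduces. Over four arms, 4 × 38 = 152 expected completers, for all of whom both exams are optional under X5.

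**3. Slit-lamp percentage among those examined.** The documents give no examination or abnormality rates, so everything from here is an assumed illustration. Let N = 38, let a be the number truly abnormal, and let r be the chance that an abnormal subject is examined divided by the chance that a normal one is. Then

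examined-only % = r·a / (r·a + N − a).

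| r | a = 2 | a = 12 |
|---|---|---|
| 1 | 2/38 = 5.3% | 12/38 = 31.6% |
| 1.5 | 3/39 = 7.7% | 18/44 = 40.9% |
| 2 | 4/40 = 10.0% | 24/50 = 48.0% |
| 4 | 8/44 = 18.2% | 48/74 = 64.9% |

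The row r = 1 gives the true percentage, so there is no bias. The column a = 12 might represent long-standing mild lid findings, which Protocol 5.4 allows at entry. For such findings r may well be near 1.

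**4. BCVA mean change among those examined.** Suppose 2 of 38 worsen by 0.22 logMAR and the rest do not change. The mean is 0.22 times the proportion in the a = 2 column: 0.012, 0.017, 0.022 and 0.040 at r = 1, 1.5, 2 and 4. The largest shift is 0.040 − 0.012 = 0.028 logMAR. At 0.02 per letter, that is 1.4 letters.

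**5. The 0.22 logMAR check.** Suppose two attendees in an arm have an unreported loss of that size, and each is examined independently with probability e. The chance that at least one is missed is 1 − e²: 0% at e = 1, 44% at 0.75, 75% at 0.5 and 94% at 0.25.

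Steps 3 and 4 concern examination driven by complaints. Step 5 concerns subjects who do not complain. They are separate scenarios and should not be added together.

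**The case against.** The strongest reply is that the discretion was intended. It appears consistently in X5, SAP 4.2, SAP 15.2 and SAP 15.3. Protocol 8.4.1 sends sites to Appendix 1 for the schedule, and Appendix 2 is mainly about technique. On that view the defect is loose wording in 8.3.1, and correcting 8.3.1 and Appendix 2 would be an equally valid remedy. This stands in part: it shows that either side could be changed, but not that the documents agree.

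Much is also covered already. Both exams are planned for everyone after the Visit 1 dose. The AE query runs before and after the CAE at Visit 2. The SAP schedule has pupil diameter measured post-CAE without X5, and acuity and slit lamp are available at unscheduled visits. The SAP also reports n and provides subject listings. All of this limits the consequence. None of it measures acuity after the second dose in a subject who reports nothing.

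A reader might go further in four ways that the documents do not support.

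- **Timing.** Appendix 2 says "Visual acuity should be evaluated at the beginning of each visit in the study", which could suggest that Visit 2 acuity is taken before the second dose. The same sentence explains the phrase as meaning ahead of the slit lamp, and 8.3.1 lists BCVA after treatment at Visit 2. A post-CAE acuity test followed by slit lamp satisfies both.
- **Denominator.** Using subjects with a result is the usual observed-data rule and is not itself an error.
- **Between-arm bias.** Treatment is masked and randomization is stratified by site, so there is no reason to expect examination rates to differ by arm.
- **A dropped analysis.** The synopsis also plans a shift to the worst on-treatment value, which the visible SAP does not carry. Protocol 10.4.7 is redacted and the SAP supersedes the protocol's methods, so nothing firm follows.

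**Conclusion.** The inconsistency is real, and its consequence is minor. Protocol 8.3.1, with Appendix 2 for slit lamp, requires Visit 2 exams that X5 and SAP 15.2/15.3 make optional, and the SAP tabulates the results without a rule for when the exam is needed or an examined-only label.

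Whether the Visit 2 results are distorted depends on site behaviour that the documents do not describe. If everyone is examined, there is no selection and the acuity check is complete. If examination covers only some but is unrelated to findings, the percentages and means are unbiased, though based on fewer subjects. If it follows complaints, they tend to be inflated by an unknown amount. The figures above show direction and sensitivity to assumed rates and are not estimates for this trial. The effect is confined to descriptive safety results at Visit 2. Primary efficacy is unaffected.

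**What to change.** **Preferred.** Remove the discretion from footnote X5 (Protocol Appendix 1 and SAP 4.2) and from SAP 15.2 and 15.3, so that BCVA and then slit lamp are done post-CAE for every subject attending Visit 2. Delete the as-needed wording for the Visit 2 intranasal examination in SAP 15.4, to match both schedules.

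**If discretion is kept, or data are already collected.** Show by arm the number examined over the number attending Visit 2, and label the Visit 2 BCVA and slit-lamp tables examined-only. Attendance is the right denominator because a subject who does not qualify in the CAE may be examined without having been dosed. If discretion is kept by choice, correct 8.3.1 and Appendix 2 to say so.

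**Cost.** A small protocol amendment, SAP wording changes, and slightly more examination time at sites that would have used the discretion. No procedure is added beyond what 8.3.1 already lists, and subjects already have intranasal and pupil assessments scheduled post-CAE.

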15.4 Intranasal Examination

The intranasal examination will be performed as needed pre-treatment at Visit 1 and post-CAE® at Visit 2. The results in terms of Normal, Abnormal (NCS), and Abnormal (CS) will be summarized using counts and percentages for each treatment group for each nasal cavity (right and left). Percentages will be based on the number of subjects in each treatment group with responses. Shift tables will also be provided comparing results post-treatment at Visit 1 to pre-treatment at Visit 1. A subject listing will also be produced.

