The examiner should instill 5 μ L of 2% preservative-free sodium fluorescein solution into the inferior conjunctival cul-de-sac of each eye. Alternatively, corneal staining can be assessed using 1.0 mg sodium fluorescein strips. After moistening the tip of the strip with sterile buffered saline, the excess is shaken into a waste bin with a sharp flick. The lower lid is then pulled down and the flat end of the tip should be gently applied to the inferior tarsal conjunctiva with the intent of not inducing reflex tearing and instilling a very small volume of dye.

The participant will be instructed to blink naturally several times without forced closure of the eyelid to distribute the fluorescein. In order to achieve maximum fluorescence, the examiner should wait at least two minutes after instillation before evaluating corneal fluorescein staining. A Wratten #12 yellow filter will be used to enhance the ability to grade fluorescein staining. The staining will be graded with the NEI Scale. The upper eyelid is lifted slightly to grade the entire corneal surface.

NEI/Industry Workshop Scale

Score each of five areas on the cornea of each eye.

[figure not shown]

Diagram of the division of the corneal surface for measuring fluorescein uptake. A standardized grading system of 0-3 is used for each of the five areas on each cornea. Grade 0 will be specified when no staining is present. The maximum score is 15.

Intranasal Examination

Qualified participants for the study must undergo a nasal endoscopy exam to make the final eligibility determination (e.g. severe nasal airway obstruction such as, severe septal deviation or inferior turbinate hypertrophy, or vascularized polyp seen on examination are reasons for exclusion). To monitor nasal mucosal integrity during the study for participant safety, an examination of the nasal cavities via an endoscopic camera will be performed at the Screening Visit (after all other screening procedures have been completed). This examination will be performed by an Ear Nose and Throat (ENT) specialist, otolaryngologist or other suitably qualified medical practitioner (i.e. one who has been trained to perform nasal endoscopy). Still images or video may be captured. Participants should be instructed not to perform nasal stimulation on the day nasal endoscopy will be performed.

Schirmer's Test with Topical Anesthesia

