4.2 Schedule of Visits and Assessments

The schedule of visits and assessments is provided below.

Procedure	Visit 1 (Day 1)		Visit 2 (Day 15 + 4)	
	Screening	Schirmer's Test Evaluation	Pre-CAE®	Post-CAE®
Informed consent/HIPAA	X			
Demographics	X			
Medical/Medication, ocular history and updates	X		X	
Eligibility criteria	X			
Urine pregnancy test	X ₃		X ₃	
OSDI® questionnaire	X			
Eye Dryness Score (EDS)	X		X ₄	X ₄
██████ Ocular Discomfort Scale	X		X ₄	X ₄
BCVA	X	X ₁		X ₅
Slit-lamp biomicroscopy	X	X ₁		X ₅
Corneal fluorescein staining	X			
Schirmer's test	X	X ₁		
Schirmer's test with cotton swab stimulation	X			
Intranasal examination	X	X ₁		X
Pupil diameter measurement	X	X ₁		X
Concomitant medications	X	X ₁		X

Randomization		X		
Administer investigational drug / placebo		X ₂	X	
AE Query	X	X ₁	X	X
Exit from study				X
X₁ = Post-treatment procedures; X₂ = Concurrent with Schirmer's Test; X₃ = For females of childbearing potential; X₄ = Procedure started at time 0 and then conducted every 5 minutes thereafter during the 120 minute CAE [®] exposure; X₅ = Procedure may be performed after CAE [®] exit at the Investigator's discretion as needed				

5. Study Treatments

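### The intranasal shift table in SAP 15.4 stops at Visit 1, so no planned table shows within-subject nasal change to the scheduled Visit 2 examination

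*SAP*

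**What the plan says.** SAP 15.4 opens with the timing: "The intranasal examination will be performed as needed pre-treatment at Visit 1 and post-CAE® at Visit 2". It then plans counts and percentages of Normal, Abnormal NCS and Abnormal CS for each nasal cavity and arm, and defines the shift: "Shift tables will also be provided comparing results post-treatment at Visit 1 to pre-treatment at Visit 1". The list in SAP section 20 has two intranasal tables, 14.3.4.1 (results) and 14.3.4.2 (shift). Neither title names a time point.

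The row "Intranasal examination" in SAP 4.2, and the same row in Protocol Appendix 1, mark three examinations: screening, Visit 1 post-treatment and Visit 2 post-CAE. The Visit 2 mark is a plain X. The footnote beginning "Procedure may be performed after CAE® exit", which leaves a procedure to the investigator's judgement, is attached to visual acuity and slit lamp at Visit 2 but not to the nose. Protocol 8.3.1 lists "Intranasal endoscopic examination" among the Visit 1 post-treatment procedures and "Intranasal Examination" among the Visit 2 procedures.

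For the slit lamp, SAP 15.3 plans shift tables "comparing post-treatment at Visit 1 and post-CAE® at Visit 2 to baseline". SAP 15.2 (visual acuity) and 15.5 (pupil diameter) plan change from baseline by visit.

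**The concern.** The product is a nasal spray. Protocol Appendix 2 introduces the nasal examination with the words "To monitor nasal mucosal integrity during the study for participant safety". Visit 2 is the only scheduled nasal examination after Day 1. It is also the only one after the second dose, for subjects who qualify for that dose during the CAE. Yet the nose is the one examination-based safety measure for which the SAP plans no comparison with baseline at Visit 2.

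At stake is how nasal tolerability is reported by arm. A subject who moves from Normal to an abnormal grade between screening and Visit 2, without an adverse event being recorded, would be visible only by reading Listing 16.2.8.3 line by line. Protocol Appendix 2 tells the investigator to consider an adverse event when logMAR worsens by 0.22 or more. The visible text gives no such prompt for a change in nasal grade, so the adverse event tables cannot be relied on to pick it up.

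**Working it through.** **1. Examinations scheduled and comparisons planned**

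| Measure | Visit 2 mark in SAP 4.2 | Planned comparison with baseline | Reaches Visit 2? |
|---|---|---|---|
| Intranasal | X | Shift, Visit 1 post against Visit 1 pre (15.4) | No |
| Slit lamp | X5 (discretionary) | Shift, Visit 1 post and Visit 2 post-CAE (15.3) | Yes |
| Visual acuity | X5 (discretionary) | Change from baseline by visit (15.2) | Yes |
| Pupil diameter | X | Change from baseline by visit (15.5) | Yes |

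Each measure has two scheduled post-dose time points, Visit 1 post-treatment and Visit 2 post-CAE. The nose has 1 of 2 compared with baseline and the slit lamp explicitly 2 of 2. Visual acuity and pupil diameter have 2 of 2 if by-visit reporting includes both post-dose points, which the SAP implies but does not spell out.

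**2. Consistency within SAP 15.4**

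The timing sentence names two examinations, pre-treatment Visit 1 and post-CAE Visit 2. The shift sentence uses pre-treatment and post-treatment Visit 1. The post-treatment examination in the shift is therefore absent from the timing sentence, and the Visit 2 examination in the timing sentence is absent from the shift. The conditional wording of the timing sentence also conflicts with the unconditional marks in both schedules, and with Protocol Appendix 2, which makes the screening endoscopy a requirement for eligibility.

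**3. Size**

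Inputs: 40 randomized per arm, 5% dropout, four arms (Protocol 10.3); Visit 2 on Day 15 with a window of +4 (SAP 4.1); three grades and two cavities (SAP 15.4).

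- Completers per arm: 40 × (1 − 0.05) = 38, which reproduces the protocol's figure.
- Visit 2 examinations outside the shift table: 4 × 38 = 152. Results by nasal cavity: 152 × 2 = 304.
- Time from first dose to Visit 2: 15 − 1 = 14 days to 19 − 1 = 18 days. The planned shift ends on Day 1.

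**4. Whether counts can stand in for a shift**

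Let n = 38, with b subjects abnormal at baseline and f abnormal at Visit 2. The counts fix b and f only. The number newly abnormal can lie anywhere from max(0, f − b) to min(f, n − b). The documents give no nasal findings, so these values are assumed for illustration:

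| b | f | Newly abnormal | Percent of 38 |
|---|---|---|---|
| 4 | 4 | 0 to 4 | 0% to 10.5% |
| 8 | 8 | 0 to 8 | 0% to 21.1% |
| 4 | 8 | 4 to 8 | 10.5% to 21.1% |

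Identical counts at baseline and Visit 2 are compatible with no new abnormality, or with all of the abnormal subjects at Visit 2 being new. Table 14.3.4.1 cannot tell these apart.

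**The case against.** The case for leaving the plan alone has several parts.

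- **Nothing is lost.** Visit 2 grades go into Listing 16.2.8.3 and should enter the counts in Table 14.3.4.1, although SAP 15.4, unlike 15.3, does not say that counts are given at each visit. Any worsening recorded as an adverse event enters the TEAE tables. This stands, and it limits the weight of the point. It does not supply a by-arm table of graded change.
- **The protocol already foresees shifts.** The synopsis includes the intranasal examination among safety endpoints summarized by arm and visit, and allows for changes or shifts from baseline where suitable. SAP section 18 declares no departure from this. The synopsis wording is permissive, however, and SAP section 1 says that SAP methods take precedence. The programmer will follow 15.4.
- **Text is missing.** Protocol 10.4.7 is redacted, and the title of Table 14.3.4.2 names no time point, so the restriction rests on one SAP sentence. That is so, but the sentence is explicit and the SAP governs.
- **The purpose statement is weaker than it looks.** The same sentence in Appendix 2 goes on to name only the screening examination. The Visit 2 examination rests on the two schedules and Protocol 8.3.1, which are sufficient.
- **Visit 2 mixes exposures.** The second dose is given only to subjects who reach the discomfort threshold in the CAE, so a Visit 2 shift pools subjects just dosed again with subjects last dosed on Day 1. This is a fair caution about interpretation. It is not a reason to leave out the only examination that follows the second dose.
- **The choice may be deliberate.** An acute, Visit 1-only shift is conceivable in a two-dose study. The visible text gives no rationale, and the slit lamp is handled differently one section earlier.

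**Conclusion.** The point holds. As written, SAP 15.4 leaves the scheduled Visit 2 nasal examination out of the only within-subject nasal analysis, and its timing sentence conflicts both with the schedules and with its own shift table. The size is about 152 examinations (304 cavity results) outside one descriptive table, and 1 of 2 scheduled post-dose time points compared with baseline. The 152 assumes 5% dropout and that every completer is examined at Visit 2. It counts results outside a table and does not measure lost data. The documents do not show whether the Visit 1-only wording was intended. The consequence is confined to descriptive safety reporting, so this is a low-cost improvement and not a flaw in the trial's main conclusions.

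**What to change.** In SAP 15.4, extend the shift to compare both the Visit 1 post-treatment and the Visit 2 post-CAE examinations with the pre-treatment Visit 1 result, by arm and nasal cavity, in line with SAP 15.3. State the time points in the title or shell of Table 14.3.4.2. A footnote giving the number in each arm who received the second dose would help readers interpret the Visit 2 columns.

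Reconcile the first sentence of SAP 15.4 with SAP 4.2, Protocol Appendix 1 and Protocol 8.3.1, on both the conditional wording and the unnamed Visit 1 post-treatment examination.

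The cost is two sentences in the SAP and 3 × 3 grades × 2 cavities × 4 arms = 72 extra cells in one table. No new examination, data item or test is needed. With about 38 subjects per arm many cells will be small, so the table should stay descriptive.
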